8.3 Dropouts

If a subject withdraws from the study, if the date of an adverse event is not available and a determination of whether or not the event is treatment emergent cannot be made, by convention the event will be considered to be treatment emergent.

8.4 Visit Windows

Assessments taken outside of protocol allowable windows will be displayed according to the case report form (CRF) assessment recorded by the investigator.

8.5 Early Termination Assessments and Follow-up Assessments

When a patient withdraws from the study prematurely for any reason, an early termination (ET) visit is to be performed, except in the case when a patient withdraws consent (and the protocol specifically states that no further data would be collected). An ET visit should be “on treatment,” and efficacy data collected at the ET visit are suitable for use in statistical analysis. Any data collected 45 or more days after last dose of investigational product (IP)_ will be considered “off treatment”.

8.6 Unscheduled Assessments

Extra assessments (laboratory data or vital signs associated with non-protocol clinical visits or obtained in the course of investigating or managing adverse events) will be included in listings, but not summaries. If more than one laboratory value is available for a given visit, the observation identified by the investigator to be the scheduled assessment will be used in summaries; all observations will be presented in listings.

Data from unscheduled assessments will be included in longitudinal data summaries (e.g., minimum, maximum over time). Data planned at scheduled times for which unscheduled assessments are taken will not be reflected in by-visit summaries.

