7.1.6.3 Assessment of Potential Cases of Drug Induced Liver Injury

Abnormal values in aspartate transaminase (AST) and/or alanine transaminase (ALT) concurrent with abnormal elevations in total bilirubin that meet the criteria outlined below, in the absence of other causes of liver injury, are considered potential cases of drug-induced liver injury. These events should be considered important medical events and reported as serious adverse events.

Participants who present with the following laboratory abnormalities should be evaluated further to definitively determine the etiology of the abnormal laboratory values:

- a. Participants with AST or ALT baseline values within the normal range who subsequently present with AST or ALT ≥ 3 times the upper limit of normal concurrent with a total bilirubin ≥ 2 times the upper limit of normal with no evidence of 1) hemolysis, 2) cholestasis (elevated alkaline phosphatase ≥ 2 times the upper limit of normal or not available) or 3) Gilbert's Syndrome (common benign condition associated with intermittent elevations of primarily indirect, unconjugated, bilirubin to about 2 X upper limit of normal.)

b. Participants with pre-existing AST or ALT baseline values above the normal range who subsequently present with AST or ALT ≥ 2 times the baseline values and ≥ 3 times the upper limit of normal concurrent with a total bilirubin ≥ 2 times the upper limit of normal with no evidence of 1) hemolysis, 2) cholestasis (elevated alkaline phosphatase ≥ 2 times the upper limit of normal or not available) or 3) Gilbert's Syndrome (common benign condition associated with intermittent elevations of primarily indirect, unconjugated, bilirubin to about 2 X upper limit of normal.)

Increases defined above should be confirmed with repeat testing within 48 to 72 hours. In addition to repeating AST and ALT, laboratory tests should include albumin, amylase, creatine kinase, total bilirubin, direct and indirect bilirubin, gamma-glutamyl transferase (GGT), international normalized ratio (INR) and alkaline phosphatase. Symptoms should be assessed. The medical monitor should be contacted to discuss the patient's condition.

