6.9.4 Routine Clinical Laboratory Measurements

Because “exacerbations” of pre-existing abnormalities in laboratory analytes are examined using clinical judgment and are reported as TEAEs, additional analysis on TEAVs is limited to subjects with values that are normal prior to dosing and abnormal after dosing. Potentially

clinically significant abnormalities in laboratory analytes are to be reported as TEAEs and summarized as clinical TEAEs.

Subjects with clinical laboratory data meeting the criteria in Section 10 of this SAP for values of potential clinical concern will be identified and summarized. Proportions of subjects with clinical laboratory values of potential clinical concern will be examined for the treatment groups.

For each post-Baseline assessment, descriptive statistics are provided for the assessment value and the change from Baseline to the assessment with mean, median, standard deviation, minimum, and maximum at each assessment time. Liver Function Tests

Liver function tests have additional analysis views for this study in accordance with current regulatory guidance. To explore the potential for drug-induced liver injury consistent with *Guidance for Industry "Drug-induced liver injury: premarketing clinical evaluation"* (CDER, CBER, July 2009), subjects will be summarized and listed who meet the following criteria:

- (1) Elevations in either AST or ALT of at least 3-times the upper limit of normal, and
- (2) An accompanying abnormal bilirubin.

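### SAP 8.6 contradicts itself on unscheduled safety data, and the SAP does not say which rule governs the subject-level laboratory, vital-sign and liver-criteria counts

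*SAP*

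**What the plan says.** SAP 8.6 (Unscheduled Assessments) has two paragraphs.

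- **First paragraph.** Extra laboratory or vital-sign data from non-protocol visits, or "obtained in the course of investigating or managing adverse events) will be included in listings, but not summaries". When a visit has more than one laboratory value, "the observation identified by the investigator to be the scheduled assessment will be used in summaries; all observations will be presented in listings".
- **Second paragraph.** "Data from unscheduled assessments will be included in longitudinal data summaries (e.g., minimum, maximum over time"), followed by "Data planned at scheduled times for which unscheduled assessments are taken will not be reflected in by-visit summaries".

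The tables at issue are defined elsewhere, and all count subjects:

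- SAP 5.2.5: subjects with a treatment-emergent abnormal value (TEAV), with a TEAV of potential clinical concern, or with a TEAV in a liver function test.
- SAP 6.9.2 and 6.9.4: proportions of subjects with vital signs or laboratory values of potential clinical concern.
- SAP 6.9.4, liver function tests: "subjects will be summarized and listed who meet the following criteria", namely "Elevations in either AST or ALT of at least 3-times the upper limit of normal, and" an accompanying abnormal bilirubin.

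None of these definitions is tied to a visit, limited to scheduled draws, or linked to either paragraph of 8.6.

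**The concern.** The restriction in the first paragraph is not confined to by-visit tables, and it names adverse-event work-up explicitly. The inclusion in the second paragraph is general and gives only minimum and maximum as examples. A programmer could follow either one, and SAP 8.8 requires all summaries to be produced according to the plan. Two people could therefore both comply and report different numbers of subjects meeting the liver criteria.

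This matters because scheduled sampling is sparse. For a Part 1 completer, Protocol Table 1 gives two post-dose laboratory draws in the treatment period, Months 3 and 6, and one at follow-up. Apart from an early-termination visit, any other abnormality is seen only on an extra draw. If such draws are left out, the subject-level counts can miss people whose only qualifying value came from a work-up.

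**Working it through.** The plan states no figure on this point, so the check compares the texts and then applies the thresholds.

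**Step 1. Which tables does each rule reach?**

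| Table | First paragraph of 8.6 | Second paragraph of 8.6 |
|---|---|---|
| By-visit means and changes | extra values out | extra values out |
| Minimum or maximum over time | work-up labs and vitals out | extra values in |
| Subjects with a TEAV, a value of concern, or the liver criteria | work-up labs and vitals out | not named; in, if treated as worst value over time |

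The paragraphs agree on the first row, conflict on the second, and leave the third unassigned. The rule for several laboratory values at one visit adds to the problem. Visit windows are ±7 days, so a repeat taken 48 to 72 hours later can fall inside the same window and be set aside in favour of the value labelled scheduled.

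**Step 2. Does losing the protocol's confirmatory liver test lose a subject?** Inputs, in multiples of ULN:

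- Protocol 7.1.6.3 trigger: "AST or ALT ≥ 3 times the upper limit of normal concurrent with a total bilirubin ≥ 2 times the upper limit of normal". After that, "Increases defined above should be confirmed with repeat testing within 48 to 72 hours".
- SAP 6.9.4 criterion: AST or ALT ≥ 3 and bilirubin abnormal, taken here as > 1 (assumption: abnormal means above ULN).
- SAP Section 11 limits of concern: AST or ALT > 3; total bilirubin > 1.5.

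Bilirubin ≥ 2 implies bilirubin > 1 and > 1.5, so every pair of values that meets the protocol trigger also meets the SAP liver criterion and at least one limit of concern. A grid from 0.5 to 10 in steps of 0.1 confirms this:

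- Protocol trigger: 71 ALT values × 81 bilirubin values = 5,751 points, all of which meet the SAP liver criterion and a limit of concern.
- SAP liver criterion: 71 × 90 = 6,390 points.
- Difference: 6,390 − 5,751 = 639 points that meet the SAP criterion without the protocol trigger (bilirubin 1.1 to 1.9).

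If the triggering draw was scheduled, the subject is already counted and omitting the repeat changes nothing.

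**Step 3. When does a subject drop out of the count?** When the first qualifying value is on an extra draw. Illustrative values:

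- Scheduled draw: ALT 3.5, bilirubin 0.9. The ALT part is met (3.5 ≥ 3) and the bilirubin part is not (0.9 is below 1).
- Extra draw: ALT 4.0, bilirubin 1.8. Both parts are met.
- Scheduled values only: not counted for the liver criteria, nor for bilirubin of concern (1.8 > 1.5). ALT of concern is still counted, from the scheduled 3.5.
- All values: counted in each.

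Neither draw reaches the protocol trigger (0.9 and 1.8 are both below 2), so the extra draw is not the repeat that Protocol 7.1.6.3 requires.

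**Step 4. Direction and size.** An ever-met count on a subset of values cannot exceed the count on all values, so the first paragraph can only lower a count or leave it unchanged. SAP 1.4 gives 43 enrolled. Assuming arms of 21 and 22, one omitted subject is 1/22 = 4.5% or 1/21 = 4.8% of an arm.

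**The case against.** **The intended rule can be guessed.** The second paragraph puts unscheduled data into worst-value summaries and names by-visit tables as the place for exclusion. A subject-level ever-met count is closest in kind to a maximum over time. That is a reasonable reading, but it is an inference: nothing in the SAP states it, and the more specific sentence points the other way.

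**Other routes exist.** SAP 6.9.4 has potentially clinically significant laboratory abnormalities reported and summarized as TEAEs. Protocol 7.1.6.3 has potential drug-induced liver injury reported as serious adverse events. SAP 5.2 has safety listings reviewed by medically qualified people. This stands, and it lowers the risk that a serious case goes unseen. It does not repair the threshold-based counts, which are planned separately (Protocol 9.8.1.3 lists the liver-injury proportion as its own variable). The Step 3 subject would not meet the Protocol 7.1.6.3 definition, because bilirubin stays below 2 times ULN.

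**A stronger reading is tempting.** A reader might infer that the protocol's repeat liver tests are barred from all summaries and that liver signals are therefore under-counted. The documents do not support this. The second paragraph contradicts a bar on all summaries, and by Step 2 the required repeat follows a value that already meets the SAP criterion. A reader might also extend the exclusion to QTc, but the restrictive sentence covers laboratory data and vital signs, not ECGs. Nor can the loss be sized from how seldom two scheduled draws would overlap a short abnormality: that describes the visit schedule, whereas the effect of 8.6 depends on how many subjects had a qualifying extra draw, which the documents do not give.

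**Not every value is in the database.** SAP 5.2.5 says routinely collected laboratory data that the protocol does not require will not be captured. This stands and limits the fix to captured values.

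**Conclusion.** The contradiction is real and should be resolved before the treatment-period data are locked and unblinded, so that the rule is not chosen with cases in view. It is not a demonstrated bias. Under-counting requires both that the first paragraph is applied to the subject-level tables and that a subject's first qualifying value sits on an extra draw. When both hold, the count is too low, by about 4.5 to 4.8 percentage points of an arm per subject (assuming 21 or 22 per arm). The number of such subjects is unknown and may be zero. Subjects whose scheduled draw already qualified are unaffected.

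**What to change.** Rewrite SAP 8.6 to say three things:

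1. Unscheduled laboratory and vital-sign values are excluded from by-visit summaries only. The listings-only wording is removed for all other tables.
2. Subject-level ever-met tables (TEAVs, laboratory and vital-sign values of potential clinical concern, the liver criteria in 6.9.4) and minimum/maximum summaries use every post-dose value captured in the study database, scheduled or unscheduled. Where a visit has more than one value, choosing the scheduled one applies to the by-visit table alone.
3. The same convention applies to the QTc categories in 6.9.5, for consistency.

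The cost is one paragraph of text and a programming flag, with no new data collection. The one downside is that subjects tested more often have more chances to be flagged, so the number of tests per arm should be shown beside these counts.

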8.7 Values Below LLQ

Concentrations for TTP488 and metabolites below the lower limit of quantification (LLQ) for the assay will be set to zero for the purpose of analysis.

8.8 Analysis Deviations

All statistical analyses and summary information will be generated according to this analysis plan. Any deviation from this plan will be documented in the clinical study report. Exploratory analyses are permitted per protocol; those analyses will not be considered to be deviations.

9 Software

All analyses will be done using SAS Version 9.3 or later.

10 Data Displays

The plans for displaying data will conform to this guideline and also to ICH E3 (*Structure and Content of clinical Study Reports*), and to ICH E9 (*Statistical Principles for Clinical Trials*).

The following excerpt from ICH E3 (1996) applies to this SAP:

“The guidance provided below is detailed and is intended to notify the applicant of virtually all of the information that should routinely be provided so that post-submission requests for further data clarification and analyses can be reduced as much as possible. Nonetheless, specific requirements for data presentation and/or analysis may depend on specific situations, may evolve over time, may vary from drug class to drug class, may differ among regions and cannot be described in general terms; it is therefore important to refer to specific clinical guidelines and to discuss data presentation and analyses with the reviewing authority, whenever possible. Detailed written guidance on statistical approaches is available from some authorities.

“Each report should consider all of the topics described (unless clearly not relevant) although the specific sequence and grouping of topics may be changed if alternatives are more logical for a particular study” (p. 2).

In accordance with FDA and ICH guidance, tables, figures, and key data listings are planned. Exploratory and data-driven data displays may also be generated.

In addition to the data summaries and listings, the set of displays will include clinical laboratory normal ranges (with units) and also a display of the MedDRA mapping glossary, which will display the verbatim text as reported by the investigator, the LLT, PT, and SOC.

11 Values of Potential Clinical Concern

Criteria for Safety Values of Potential Clinical Concern

Hematology

| Assay | Lower limit of the normal reference range (LLN) | Upper limit of the normal reference range (ULN) |
|-------------------------|---|---|
| Hemoglobin | <0.8 times | >1.2 times |
| Hematocrit | <0.8 times | >1.2 times |
| RBC | <0.8 times | |
| Platelets | <0.5 times | >1.75 times |
| WBC | <0.6 times | >1.5 times |

| Sign informed consent / provide assent ^d | X | | | | | | | | | |
| Assessment of continued consent/assent | | X | | | | X | | | X | X |
| Assign Screening ID | X | | | | | | | | | |
| Randomization | | | X | | | | | | | |
| Demographic information | X | | | | | | | | | |
| Review Inclusion/Exclusion Criteria | X | X | X | | | | | | | |
| Medical History/Surgical History / Drug, Alcohol, Tobacco Use History | X | | | | | | | | | |
| Complete Neuro Exam & Physical Exam | X | | | | | | | | | |
| Height | X | | | | | | | | | |
| ApoE genotyping | | X | | | | | | | | |
| Telephone Contact | | | | X | X | | X | X | | |
| Body weight | X | X | | | | X | | | X | X |
| BMI calculation | X | | | | | | | | | |
| Brief Neuro & Physical Exams | | X | | | | X | | | X | X |
| Review Concomitant Medications | X | X | | X | X | X | X | X | X | X |
| Blood Pressure and Pulse Rate (supine) ^e | X | X ^e | | | | X | | | X | X |
| 12 Lead ECG ^e | X ^f | X ^e | | | | X | | | X | X |

| Protocol Activity | Screening | Baseline | Treatment Period ^a | | | | | | | Follow-up ^b |
|---|-------------------|-----------------|-------------------------------|---------|---------|---------|---------|---------|----------------|--------------------------|
| | Day -60 to Day -1 | Day -7 to Day 1 | Day 1 ^c | Month 1 | Month 2 | Month 3 | Month 4 | Month 5 | Month 6 / ET | 3 months after last dose |
| Study Days | -60 to -1 | -7 to 1 | 1 | 30 | 60 | 90 | 120 | 150 | 180 or ET | 270 |
| Window | | | | ±7d | ±7d | ±7d | ±7d | ±7d | ±7d | ±7d |
| Adverse Events Assessment | | X | | X | X | X | X | X | X | X |
| Dispense / Return Study Drug / Drug Accountability | | | X | | | X | | | X | |
| Study Drug Dosing ^{a,c} | | | X | → | → | → | → | → | | |
| MMSE ^g | X | X | | | | X | | | X ^h | X |
| ADAS-cog14 ^g | X | X | | | | X | | | X ^h | X |
| CDR ^g | X | X | | | | X | | | X ^h | X |
| FAQ | | X | | | | X | | | X ^h | X |
| Amsterdam-IADL | | X | | | | X | | | X ^h | X |
| Columbia Suicide Severity Scale (C-SSRS) ⁱ | X | X | | | | X | | | X | X |
| Fasting Central Lab Blood and Urine Collection ^j | X | X | | | | X | | | X | X |
| Urine Drug Screen | X | | | | | | | | | |
| Provide meal/snack ^k | X | X | | | | X | | | X | X |
| Blood glucose measurement ^l | X | X | | | | X | | | X | X |
| Brain MRI ^m | X | | | | | | | | | |
| Blood Sample for PK, PD and Plasma Retention and Storage | | X | | | | X | | | X | X |

a Participants will receive azeliragon 5 mg once daily, or matching placebo during the treatment period.

b Follow-up visit required for all participants who dosed with study medication. A Follow-up Visit should be completed 3 months after a subject completes Month 6 for those participants who complete the study; or at least 45 days after the last dose of study drug if the subject discontinues the study prior to Month 6.

c Subject begins taking study medication in the clinic as soon as baseline procedures are completed, and eligibility confirmed. Date of first dose is noted as Day 1.

d Where assent is in accordance with local laws, regulations and ethics committee policy.

e Vitals and ECG will be measured in triplicate at Baseline and as single values at all other times. An average of the three measurements for ECG and blood pressure will be used for eligibility determination.

f ECG at Screening visit repeated if QTc > 470 msec.

g Neuropsychological assessments are not to be performed with fasted participant; ensure participant has been fed and meets blood glucose measurement requirements prior to any neuropsychological assessments.

h Neuropsychological assessments are performed at the Early Termination Visit only when the visit is within 30 days of the last dose of study drug.

- i C-SSRS is administered to subject jointly with caregiver.
- j Blood Chemistry sample is collected in a fasted state (8-hour fast).
- k Provide a low carbohydrate/high protein meal or snack *after* fasting blood samples are drawn and *before* any neuropsychological assessments are performed.
- l Blood glucose measurement is an in-office point of care measurement after an appropriate period following the meal/snack, and prior to neuropsychological assessments are performed.
- m CT scan may be utilized for subjects with contraindication to MRI. MRI or CT should be done at least 14 days prior to the baseline visit to allow time for MRI report to support eligibility decision.

[figure not shown]

Figure 1. Statistical Hypothesis Schematic
